Primary endpoint (COVID-adjusted Composite estimand)	Responder if: 
 • Free of post-baseline transfusion within the range of Week 5 and Week 26 visit dates, and • The change from baseline in Hgb at treatment assessment timepoint ≥ 1.5 g/dL, and • Receive no protocol prohibited medications defined in Section 5.1.1 within the range of Week 	FAS	
 • Subjects who early discontinue study prior to Week 23, for reasons other than COVID-19, are considered non-responders • Subjects with no Hgb data from Week 23, 25, and 26, for reasons other than COVID-19, are considered as non-responders 	
 • odds ratio of the proportion of responders in BIVV009 and placebo, using stratified Cochran-Mantel-Haenszel test • Multiple imputation will be performed to fill in Hgb data at TAT using an MMRM approach, for subjects missing infusions at Week 23

Endpoint Category (estimand)	Estimands			Population-level summary (Analysis and missing data handling)
	Endpoint	Population	Intercurrent event(s) handling strategy	
	5 and Week 26 visit dates (excluding medications taken during a COVID-related infusion gap or within the following 5 weeks)		
 If a subject has a COVID-related infusion gap (defined as 2 consecutive missed infusions due to COVID-19), transfusions received and protocol-prohibited CAD medications taken during the infusion gap and within the 5 weeks following the infusion gap will not be included in the responder derivation. 	and 25 due to COVID-19
Primary endpoint (Composite estimand)	Responder if: 
 Free of post-baseline transfusion within the range of Week 5 and Week 26 visit dates, and The change from baseline in Hgb at treatment assessment timepoint ≥ 1.5 g/dL, and Receive no protocol prohibited medications defined in Section 5.1.1 within the range of Week 5 and Week 26 visit dates 	FAS	
 Subjects who early discontinue study prior to Week 23 are considered as non-responders Subjects with no Hgb data from Week 23, 25 and 26 are considered as non-responders 	odds ratio of the proportion of responders in BIVV009 and placebo, using stratified Cochran-Mantel-Haenszel test

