these visits, it will be calculated as the average of the available values, unless no value is available from all three visits.

COVID-related infusion gap

COVID-related infusion gap is defined as 2 or more consecutive missed scheduled infusions due to COVID-19. For the primary endpoint analysis, transfusions and protocol-prohibited CAD medications received during a COVID-related infusion gap and within the first 5 weeks of infusion resumption will not preclude a subject from being a responder.

Solicited Symptomatic Anemia

The severity of CAD symptomatic anemia is defined in [Table 5](#). The severity grading for symptomatic anemia is adopted based on Common Toxicity Criteria for Adverse Events (CTCAE) grades and is collected in eCRFs at every visit.

Table 5 - Severity grade for symptomatic anemia related CAD

CAGD Symptomatic Anemia Term	Grade 1	Grade 2	Grade 3	Grade 4
Fatigue	Fatigue relieved by rest	Fatigue not relieved by rest; limiting instrumental ADL	Fatigue not relieved by rest; limiting self care ADL	Not defined
Weakness	Uneasiness or lack of well being	Uneasiness or lack of well being; limiting instrumental ADL	Not defined	Not defined
Shortness of Breath	Shortness of breath with moderate exertion	Shortness of breath with minimal exertion; limiting instrumental ADL	Shortness of breath at rest; limiting self care ADL	Life-threatening consequences; urgent intervention indicated
Palpitations, fast heart beat	Mild symptoms; intervention not indicated	Intervention indicated	Not defined	Not defined
Lightheadedness	Not defined	Present (eg, near fainting)	Not defined	Not defined
Chest Pain	Mild pain	Moderate pain; limiting instrumental ADL	Pain at rest; limiting self care ADL	Not defined

ADL = activities of daily living

Thromboembolic Events

The thromboembolic events prior to study entry are recorded as medical history in the eCRFs, notably pre-specified categories of TE events occurring within 1 year prior to screening are captured, while thromboembolic events on study are captured as adverse events. Both medical history and adverse events will be coded according to Medical Dictionary for Regulatory Activities (MedDRA) v20.1 (or higher).

In general, thromboembolic events may include but are not limited to:

- Any venous events
 - Portal vein obstruction
 - Deep vein thrombosis
 - Pulmonary embolism
 - Mesenteric (abdominal) venous thrombosis
- Any cerebral events

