4.3.2 Main analytical approach

The primary analysis of the primary endpoint is to compare the responder rate of the BIVV009 treatment arm with the placebo treatment arm via the COVID-adjusted Composite estimand as defined in [Table 6](#) below.

To reject the null hypothesis of no treatment difference, the two-sided p-value based on a stratified Cochran-Mantel-Haenszel (CMH) test must be < 0.05 . The test will be stratified by baseline hemoglobin ($<$ median baseline Hgb vs \geq median baseline Hgb) and geographic region (Japan/Australia, United States, Europe). In the case of completely unbalanced strata (all records within any strata fall within a single treatment arm), the CMH test will be stratified only by baseline hemoglobin.

Table 6 - COVID-adjusted composite estimand for primary analysis

COVID-adjusted Composite Estimand	
Population	FAS
Response variable	Responder if

COVID-adjusted Composite Estimand	
	
 Free of post-baseline transfusion within the range of Week 5 and Week 26 visit dates, and The change from baseline in Hgb at treatment assessment timepoint ≥ 1.5 g/dL, and Receive no protocol prohibited medications defined in Section 4.1 within the range of Week 5 and Week 26 visit dates
ICEs handling	
 Subjects who early discontinue study prior to Week 23, for reasons other than COVID, are considered non-responders Subjects with no Hgb data from Week 23, 25, and 26, for reasons other than COVID, are considered as non-responders If a subject has a COVID-related infusion gap (defined as 2 consecutive missed infusions due to COVID-19), transfusions received and protocol-prohibited CAD medications taken during the infusion gap and within the 5 weeks following the infusion gap will not be included in the responder derivation.
Measure of treatment effect	
 Odds ratio of the proportion of responders in BIVV009 and Placebo using the Cochran-Mantel-Haenszel test Subjects missing infusions at Week 23 and 25 due to COVID will have their Hgb at TAT imputed using multiple imputation with an MMRM approach.

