Multiple imputation (n=100 imputations) will first be run on subjects who missed both the Week 23 and 25 study visits due to COVID-19 to fill in their missing Hgb data at TAT. A CMH test will be conducted on each imputation and the chi-square statistics will be pooled using Rubin's Rules, together with the pooled CMH odds ratio and a 95% confidence interval for the odds ratio will be computed.

In addition, the proportion of subjects who meet each of the three response criteria will be summarized by treatment group. A separate table for the number of transfusions by study period (before Week 5 and between Week 5 and Week 26) and by treatment arm will be generated.

If there are no patients who missed both the Week 23 and 25 study visits due to COVID-19, the primary efficacy analysis would be completed using the Composite estimand ([Section 4.3.3.1](#)).

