4.3.3.1 Sensitivity Analysis I - Composite estimand

The purpose of this sensitivity analysis is to assess the primary endpoint without adjusting for COVID-related ICEs. This analysis will compare the responder rate of the BIVV009 treatment arm with the placebo treatment arm via the Composite estimand as defined in [Table 7](#) below.

Table 7 - Composite estimand for primary analysis

Composite Estimand	
Population	FAS
Response variable	Responder if 
 • Free of post-baseline transfusion within the range of Week 5 and Week 26 visit dates, and • The change from baseline in Hgb at treatment assessment timepoint ≥ 1.5 g/dL, and • Receive no protocol prohibited medications defined in Section 4.1 within the range of Week 5 and Week 26 visit dates
ICEs handling	
 • Subjects who early discontinue study prior to Week 23 are considered as non-responders • Subjects with no Hgb data from Week 23, 25 and 26 are considered as non-responders
Measure of treatment effect	Odds ratio of the proportion of responders in BIVV009 and Placebo using the Cochran-Mantel-Haenszel test

A stratified CMH test will be used to estimate the treatment effect; the p-value for the comparison, together with the CMH odds ratio and a 95% confidence interval for the odds ratio will be reported. As with the primary endpoint, the test will be stratified by baseline hemoglobin ($<$ median baseline Hgb vs \geq median baseline Hgb) and geographic region (Japan/Australia, United States, Europe). In the case of completely unbalanced strata (all records within any strata fall within a single treatment arm), the CMH test will be stratified only by baseline hemoglobin.

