4.3.3.2 Sensitivity Analysis II - Modified composite estimand

The purpose of this sensitivity analysis is to assess the potential impact of the COVID-19 pandemic to this study by analyzing the primary efficacy endpoint with subjects did not miss any visits or discontinue early due to the COVID-19 pandemic.

This sensitivity analysis will be carried out via a modified composite estimand, which is the same as the composite estimand except with the mFAS population. A stratified CMH test will be used to estimate the treatment effect; the p-value for the comparison, together with the CMH odds ratio and a 95% confidence interval for the odds ratio will be reported. As with the primary endpoint, the test will be stratified by baseline hemoglobin ($<$ median baseline Hgb vs \geq median baseline Hgb) and geographic region (Japan/Australia, United States, Europe). In the case of completely unbalanced strata (all records within any strata fall within a single treatment arm), the CMH test will be stratified only by baseline hemoglobin.

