4.3.3.4 Sensitivity Analysis IV - Per protocol estimand

The purpose of this sensitivity analysis is to evaluate the primary endpoint with subjects who have no important protocol-deviations which potential impact efficacy assessment (the per protocol set). Subjects with protocol-prohibited medication use are excluded from the PP set. Subjects with at least 2 consecutive, or at least 3 intermittent missing dose for any reason including COVID-19, are also excluded.

This sensitivity analysis will be carried out via a per protocol estimand, which is the same as the composite estimand except with the PP set. A stratified CMH test will be used to estimate the treatment effect; the p-value for the comparison, together with the CMH odds ratio and a 95% confidence interval for the odds ratio will be reported. As with the primary endpoint, the test will be stratified by baseline hemoglobin ($<$ median baseline Hgb vs \geq median baseline Hgb) and geographic region (Japan/Australia, United States, Europe). In the case of completely unbalanced strata (all records within any strata fall within a single treatment arm), the CMH test will be stratified only by baseline hemoglobin.

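### The fallback in SAP 4.3.2 can drop the COVID infusion-gap waiver from the primary analysis on a condition that looks only at the Week 23 and Week 25 visits

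*SAP*

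**What the plan says.** **The waiver.** SAP Part A states it in three places, none of which makes it depend on Weeks 23 and 25.

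- Section 4.1 defines a COVID-related infusion gap as two or more consecutive scheduled infusions missed because of COVID-19. For the primary endpoint analysis it says that "transfusions and protocol-prohibited CAD medications received during a COVID-related infusion gap and within the first 5 weeks of infusion resumption will not preclude" a patient from being a responder.
- Section 1.2.1, Table 3, COVID-adjusted row, qualifies the medication criterion: "excluding medications taken during a COVID-related infusion gap or within the following 5 weeks". It also disregards transfusions in the same window.
- Section 4.3.2, Table 6, the estimand named for the primary analysis, says that such events during the gap and "within the 5 weeks following the infusion gap will not be included in the responder derivation".

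Table 6 also limits the non-response rule for dropouts: "Subjects who early discontinue study prior to Week 23, for reasons other than COVID, are considered non-responders". It imputes Hgb at the treatment assessment timepoint (TAT) for patients whose Week 23 and 25 infusions were missed because of COVID.

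**The fallback.** The text below Table 6 ends with a condition: "If there are no patients who missed both the Week 23 and 25 study visits due to COVID-19, the primary efficacy analysis would be completed". The analysis it then turns to is the one in Section 4.3.3.1 (Table 7, Composite estimand). Of that analysis the SAP says: "The purpose of this sensitivity analysis is to assess the primary endpoint without adjusting for COVID-related ICEs".

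**The other sensitivity analyses.** Analysis II uses an estimand "which is the same as the composite estimand except with the mFAS population". Analysis IV uses one "which is the same as the composite estimand except with the PP set". Analysis III (completers, Table 8) has no waiver either.

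**The concern.** The fallback condition and what it removes do not match. The condition asks whether anyone missed both late visits. That settles whether late Hgb has to be imputed, but says nothing about a gap at, say, Weeks 11 and 13. If nobody meets the condition, the whole COVID-adjusted estimand is replaced, including a waiver that may still apply to someone.

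Two consequences follow. First, one patient's response status depends on another patient's attendance. Second, Sections 1.2.1 and 4.1 and Table 6 state a rule for the primary analysis that the end of Section 4.3.2 can cancel, and no passage reconciles them.

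The units also differ. Tables 3 and 6 impute on missed infusions, while the text below Table 6 imputes, and sets the fallback, on missed visits.

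This is the confirmatory test, with 20 patients per arm, and it gates both key secondary endpoints (SAP 4.4.1.1 and 4.6).

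**Working it through.** **1. Which gaps stop the fallback.** The schedule (SAP 1.1) is Day 0, Day 7, then every 14 days to Week 25: Weeks 0, 1, 3, 5, ..., 25, which is 14 infusions. That gives 13 consecutive pairs, or 12 after the first dose. Each of the 12 is a COVID-related gap if missed because of COVID-19. Only Weeks 23+25 can stop the fallback, and only if the visits themselves were missed. The other 11 pairs, including 21+23, leave it in force.

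**2. Three patients under each rule.** Assume that no patient in the trial missed both late visits because of COVID.

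| Patient | Table 6 | Fallback (Table 7) |
|---|---|---|
| No COVID gap | Same result | Same result |
| COVID gap at Weeks 11+13, transfused in the gap, Hgb criterion met | Responder | Non-responder |
| Attended Weeks 23 and 25, not infused because of COVID | Hgb at TAT imputed | Observed Hgb used |

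If some other patient had missed both late visits, Table 6 would apply and the second patient would be a responder. For patients needing no imputation, the switch can only remove responders. For the third patient it could go either way.

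**3. Whether another analysis covers it.** Under the fallback, Sensitivity Analysis I is the primary analysis. II, III and IV contain no waiver, so no planned analysis applies it. However, the per-protocol set excludes anyone missing at least two consecutive doses, COVID included (SAP 4.2 and 4.3.3.4), so it always excludes a gap patient. The mFAS excludes anyone who missed a visit because of COVID (SAP Table 4), so it excludes the patient whenever the gap involved missed visits. In those cases the patient is left out, not scored as a failure.

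**4. Size.** Inputs: 20 per arm, 85% v 35%, two-sided 5% (Protocol 7.10). The plan's 87% power is reproduced by exact enumeration with Fisher's test (87.5%). The unstratified Mantel-Haenszel test gives 92.8% on the same inputs. The second test is used below because the planned analysis is now CMH.

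With a and b responders on BIVV009 and placebo, m = a + b, n = 20 and N = 40:

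chi-square = (a − m/2)² / V, where V = n² m (N − m) / [N² (N − 1)].

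For 17 v 7: m = 24, V = 400 × 24 × 16 / (1600 × 39) = 2.46, and chi-square = 25 / 2.46 = 10.16, p = 0.0014.

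| BIVV009 v placebo responders | p |
|---|---|
| 17 v 7 (design rates) | 0.0014 |
| 16 v 7 | 0.0045 |
| 15 v 7 | 0.012 |
| 14 v 7 | 0.029 |
| 13 v 7 | 0.061 |

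From the design rates, with placebo unchanged, four BIVV009 responders must be lost before p exceeds 0.05.

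To find how often a single patient decides the result, sum Bin(a; 20, 0.85) × Bin(b; 20, 0.35) over:
- outcomes significant at (a, b) but not at (a − 1, b): 7.4%, significance lost;
- outcomes not significant at (a, b) but significant at (a, b − 1): 3.4%, significance gained.

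**The case against.** **The specific rule governs.** The fallback is an explicit instruction in the same section as Table 6, so it can be read as qualifying the general rule in Section 4.1. That gives a programmer one executable path, and it ends at a definition without a waiver, as in Protocol Table 2. This stands: Table 7 is a legitimate estimand. It does not repair a condition that cannot detect what it removes. The protocol does not settle the matter either, because Protocol Section 7 gives the SAP precedence.

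**The reachable case is narrow.** It needs a transfusion in the waived window of an earlier COVID gap, an Hgb rise of at least 1.5 g/dL at TAT, and nobody missing both late visits. The medication half of the waiver is largely empty, since Protocol 4.1 withdraws patients requiring other CAD treatment in Part A and counts them as non-responders. This also stands.

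**The effect would be visible.** COVID-missed infusions, transfusion counts by period and each response component are reported by the plan, and two sensitivity populations leave gap patients out. This is true and helps interpretation, but exclusion is a different question from the waiver.

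**Stronger readings that the documents do not support.** A reader might infer that the switch is data-driven and inflates type I error. It is written in advance and turns on attendance, not outcome, and no inflation is shown. A reader might infer that it can only remove responders. That fails for the patient who attended both late visits without being infused. A reader might infer that every sensitivity analysis would count the affected patient as a failure. The per-protocol set never does, and the mFAS does not when visits were missed.

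**Conclusion.** The point holds as a defect of specification in the confirmatory analysis, and it should be fixed. The fallback tests whether imputation is needed but also withdraws the infusion-gap waiver, so a patient's response can turn on someone else's late visits. Under the fallback, no planned analysis applies the waiver.

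The size is uncertain and probably modest. The documents do not say how many patients are affected, and it may be none. The 7.4% and 3.4% presuppose exactly one affected responder who needs no imputation, true rates of 85% and 35%, and an unstratified test, whereas the planned test is stratified by baseline Hgb and region. They illustrate sensitivity near the significance boundary and are not the probability that the defect acts. At the design rates the result survives the loss of three BIVV009 responders.

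**What to change.** Before unblinding:

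1. Delete the fallback sentence at the end of SAP 4.3.2. Always derive primary response under Table 6, and skip only the imputation step when no subject needs it. An equivalent is to fall back to Table 7 only when no subject has any COVID-related intercurrent event, including infusions missed at Weeks 23 and 25; the two estimands then coincide.
2. Keep Table 7 as Sensitivity Analysis I.
3. Use one unit, missed infusion or missed visit, for the imputation rule in Table 3, Table 6 and the text below Table 6.

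The cost is one deleted sentence and one aligned term. No new data are needed, and if no patient is affected the result does not change.

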4.3.3 Sensitivity analysis

All sensitivity analyses are designed to evaluate the robustness of the primary efficacy results in different aspects, aiming to provide additive evidence of the treatment effect of BIVV009.

4.3.3.1 Sensitivity Analysis I - Composite estimand

The purpose of this sensitivity analysis is to assess the primary endpoint without adjusting for COVID-related ICEs. This analysis will compare the responder rate of the BIVV009 treatment arm with the placebo treatment arm via the Composite estimand as defined in [Table 7](#) below.

Table 7 - Composite estimand for primary analysis

Composite Estimand	
Population	FAS
Response variable	Responder if 
 • Free of post-baseline transfusion within the range of Week 5 and Week 26 visit dates, and • The change from baseline in Hgb at treatment assessment timepoint ≥ 1.5 g/dL, and • Receive no protocol prohibited medications defined in Section 4.1 within the range of Week 5 and Week 26 visit dates
ICEs handling	
 • Subjects who early discontinue study prior to Week 23 are considered as non-responders • Subjects with no Hgb data from Week 23, 25 and 26 are considered as non-responders
Measure of treatment effect	Odds ratio of the proportion of responders in BIVV009 and Placebo using the Cochran-Mantel-Haenszel test

A stratified CMH test will be used to estimate the treatment effect; the p-value for the comparison, together with the CMH odds ratio and a 95% confidence interval for the odds ratio will be reported. As with the primary endpoint, the test will be stratified by baseline hemoglobin ($<$ median baseline Hgb vs \geq median baseline Hgb) and geographic region (Japan/Australia, United States, Europe). In the case of completely unbalanced strata (all records within any strata fall within a single treatment arm), the CMH test will be stratified only by baseline hemoglobin.

4.3.3.2 Sensitivity Analysis II - Modified composite estimand

The purpose of this sensitivity analysis is to assess the potential impact of the COVID-19 pandemic to this study by analyzing the primary efficacy endpoint with subjects did not miss any visits or discontinue early due to the COVID-19 pandemic.

This sensitivity analysis will be carried out via a modified composite estimand, which is the same as the composite estimand except with the mFAS population. A stratified CMH test will be used to estimate the treatment effect; the p-value for the comparison, together with the CMH odds ratio and a 95% confidence interval for the odds ratio will be reported. As with the primary endpoint, the test will be stratified by baseline hemoglobin ($<$ median baseline Hgb vs \geq median baseline Hgb) and geographic region (Japan/Australia, United States, Europe). In the case of completely unbalanced strata (all records within any strata fall within a single treatment arm), the CMH test will be stratified only by baseline hemoglobin.

4.3.3.3 Sensitivity Analysis III - Completer estimand

The purpose of this sensitivity analysis is to evaluate the primary endpoint with subjects with evaluable hemoglobin data at treatment assessment timepoint, in other words, eliminating potential bias introduced by early discontinued subjects. This analysis is performed via the completer estimand as defined in [Table 8](#).

Table 8 - Completer estimand for primary analysis

Completer Estimand	
Population	A subset of FAS with those who complete treatment at least through Week 23 and have at least 1 evaluable Hgb from Week 23, 25, and 26
Response Variable	Responder if 
 • Free of post-baseline transfusion within the range of Week 5 and Week 26 visit dates and • The change from baseline in Hgb at treatment assessment ≥ 1.5 g/dL, and • Receive no protocol prohibited medications defined in Section 4.1 within the range of Week 5 and Week 26 visit dates
Treatment effect	Odds ratio of the proportion of responders in BIVV009 and Placebo using the Cochran-Mantel-Haenszel test

A stratified CMH test will be used to estimate the treatment effect; the p-value for the comparison, together with the CMH odds ratio and a 95% confidence interval for the odds ratio will be reported. As with the primary endpoint, the test will be stratified by baseline hemoglobin ($<$ median baseline Hgb vs \geq median baseline Hgb) and geographic region (Japan/Australia, United States, Europe). In the case of completely unbalanced strata (all records within any strata fall within a single treatment arm), the CMH test will be stratified only by baseline hemoglobin.

